## C.2.c.5. Phase 1: Baseline and Medication Trial

- **a. Initial Study Visit.** Participants will be trained to use CREMA and the one-week naturalistic baseline data collection period will begin following screening procedures. If it is determined that patient is ineligible based on labwork, they will be excluded and baseline procedures will end.
- **b.** Baseline Assessment (Study days 1-7). Throughout this study period, participants will come to the clinic for UDS collection. To facilitate opioid abstinence during the baseline period, we will use a standard contingency-management procedure. Participants will earn payments of \$10 for the first negative UDS and \$20 for the second. Two consecutive UDSs during the baseline week must be negative for illicit opioids in order for the subject to enter the medication treatment part of the trial. During the baseline assessment period, participants will be asked to use CREMA (described below). Subjects may have up to 10 days to provide the negative UDSs.

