- d. Lofexidine/Placebo Titration Procedures (Days 8-17). After two consecutive negative drugs screens have been obtained, participants will be randomly assigned to study medication (lofexidine or matching placebo). For the Shoreline site, medication will be dispensed by IDS and delivered to MUSC staff at that site. At the randomization visit, females will provide saliva samples for estradiol and progesterone testing. Trained study personnel will evaluate heart rate, orthostatic blood pressure, and pre-syncope and syncope signs and symptoms prior to the initiation of Lofexidine. Lofexidine will not be dispensed if the participant is found to have

one of the following on physical exam: 1) clinically significant bradycardia as determined by study physician; 2) orthostatic hypotension defined as a systolic blood pressure decrease of at least 20mm Hg or a diastolic blood pressure decrease of at least 10mm Hg within three minutes of standing; 3) participant endorsement of presyncope symptoms such as lightheadedness, muscular weakness, blurred vision, or feeling faint during the evaluation of orthostatic blood pressure; or 4) syncope (fainting) during the evaluation of orthostatic blood pressure. Participants with bradycardia, orthostatic hypotension, pre-syncope or syncope would be terminated from the study and study staff will facilitate appropriate follow-up medical care. To minimize risks of hypotension, lofexidine will be titrated over a 10-day period with 0.36 mg QDfor days 1 and 2; 0.36 mg BID for days 3 and 4; 0.36 mg TID for days 5 and 6; 0.36 mg BID and 0.72 QD days 7 and 8; 0.37 QD and 0.72 BID for days 9 and 10, and 0.72 mg TID on day 11 and throughout the rest of the study (see **Table 2**). This is the dose recommended by the regulatory agencies in England and the titration schedule is consistent with lofexidine titration in 8 published studies (Gish et al., 2010).

Table 2

| Days                                      | AM Dose (mg) | PM Dose (mg) | QHS Dose (mg |
|---|--------------|--------------|--------------|
| Days 1 and 2 (Study days 8 and 9)         |              |              | 0.36         |
| Days 3 and 4
(Study days 10 and
11) | 0.36         |              | 0.36         |
| Days 5 and 6 (Study days 12 and 13)       | 0.36         | 0.36         | 0.36         |
| Days 7 and 8 (Study days 14 and 15)       | 0.36         | 0.36         | 0.72         |

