| Days 9 and 10 (Study days 16 and 17)      | 0.36         | 0.72         | 0.72         |
| Days 11-40
(Study days 18-40)          | 0.72         | 0.72         | 0.72         |

Trained study personnel will evaluate heart rate, orthostatic blood pressure, pre-syncope and syncope signs and symptoms at all study visits during the titration period. If the study participant does not have bradycardia, orthostatic hypotension, or pre-syncope or syncope signs or symptoms as defined above, the dose of Lofexidine will be increased according to the titration schedule (**Table 2**). If bradycardia, orthostatic hypotension, or signs/symptoms of pre-syncope or syncope are identified at any point, the dose of Lofexidine will be lowered to the prior tolerated Lofexidine dose and the participant will remain at that dose for the duration of the study. At the beginning of the study, participants will be given a rescue pack of 36 tablets in case visits are missed. This will cover 3 days at the full dose.

The medical provider will inform the participant, verbally and with a take-home hand-out, of common side effects of lofexidine (dizziness, somnolence, dry mouth) and precautions to minimize risks associated with blood pressure (BP) decreases (hydration, standing up slowly). Participants will attend study visits three times a week during the induction period and throughout the study during which a UDS will be collected. The MUSC Investigational Drug Service will be responsible for randomization, will keep a record of the blind and will be available should unblinding be required. In the event that WorldMeds is unable to supply matching placebo. lofexidine tablets (supplied by US WorldMeds) will be encapsulated along with matching placebo capsules by Pitt Street Pharmacy, a specialty compounding pharmacy. Randomization will be stratified on presence/absence of other substance use as well as the presence/absence of significant childhood trauma (ACE>4).

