e. Medication maintenance and adherence monitoring (Days 18-40). Trained study personnel will evaluate heart rate, orthostatic blood pressure, pre-syncope and syncope signs and symptoms once per week following the Lofexidine titration. If bradycardia, orthostatic hypotension, or signs/symptoms of pre-syncope or syncope are identified at any point, the dose of Lofexidine will be lowered to the prior tolerated Lofexidine dose and the participant will remain at that dose for the duration of the study. Participants will record themselves taking their medications A survey link will be sent to the participant's cell phone via app alert two to three times daily, depending on where they are in the medication schedule. Video capture will occur through the CREMA app. The research coordinator will review the subjects' videos before each study visit. As discussed, we have used this

technology successfully for medication adherence monitoring. To encourage compliance, participants will receive \$10 for each day that they complete their medication adherence videos.

- **f. Intervention phase** (Study Days 18-40). During the 5-week medication phase, study participants will come in three times per week for UDSs. Blood pressure and pulse will be assessed at each visit. If the SBP < 90 mmHg and > 20% below screening value and/or DBP is < 50 mmHg and > 20% below screening value, or the individual is complaining of symptoms of hypotension, the medication dosage will be reduced. If these symptoms do not resolve, the individual will be removed from the study and followed until vital signs normalize. EKG's will be performed at Weeks 4 and 6 to monitor QT intervals. A contingency-management procedure will be implemented to facilitate study visit adherence. The payments will start at \$4 and increase by \$4 for each consecutive visit.

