Exploratory Aim 3: To evaluate the impact of lofexidine on illicit drug use in men and women with OUDs: Daily use data will be collected through morning reports via EMA and verified by urine drug screens (3 times weekly). Hypothesis 1: Lofexidine will increase the number of consecutive days abstinent as compared to placebo. Hypothesis 2: Lofexidine will be more efficacious in increasing consecutive days abstinent in women as compared to men. Time to relapse will be calculated as the days between the start of study medication (following titration; day 14) and the first day of lapse to opioid use or the laboratory stress induction day (day 40). Additionally, daily use data will be examined to determine the maximum number of consecutive days abstinent during follow up. Kaplan-Meier estimates and log-rank tests will be used to assess initial relationships between study treatment assignment and relapse while Cox proportional hazards models will be developed to assess the differential time to return to use across gender (using and appropriate interaction term). A significant interaction indicates that treatment may impact return to use time differently in women and men. Proportionality of hazards will be assessed using log-log plots and log-time interactions.

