#### b. Protections Against Risks

All study participants will be closely monitored for psychiatric and medical stability. All sessions will be conducted under the supervision of experienced personnel. If crisis intervention is necessary, senior staff will be available to evaluate the subject and provide an intervention or referral. If hospitalization is indicated, the patient will be hospitalized through the Center for Drug and Alcohol Programs at MUSC or an appropriate referral will be made. All participants will be fully informed that they may withdraw from the study at any time without penalty.

Lofexidine will be titrated over ten days when it is initiated. Participants will be seen by a medical provider on three times a week uring dosage escalation and orthostatic hypotension testing will be done. The medical provider will inform the participant, verbally and with a hand-out to take home, concerning common side effects of lofexidine (dizziness, somnolence, dry mouth) and precautions to minimize risks associated with blood pressure decreases (hydration, standing up slowly). The target dose of lofexidine is 2.16 mg per day, but if hypotension or other troublesome side effects develop, the medical provider may slow the titration for that individual. At the end of the study, medications will be tapered over a five-day period. Participants will be seen every other day during medication taper and blood pressure will be monitored.

To ensure confidentiality, all participant data will be coded by letters and/or numbers, and only the investigators will have access to the master lists of codes. All participant records will be kept in a locked cabinet in an office that will be locked at times when not in use. Participants who screen remotely and have virtual medication monitoring visits will be instructed to find a private location to conduc these visits. The research staff understands the importance of maintaining confidentiality, and this method of maintaining confidentiality has been used for several years by our research group and has been effective. All electronic databases are stored on HIPAA-compliant servers with restricted access. All co-investigators and study personnel have completed (or will complete upon hiring) training in Good Clinical Practices as mandated by NIH and the MUSC IRB.

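### Exploratory Aim 3 starts the time-to-relapse clock on day 14, which on the protocol's own schedule is neither the start of medication nor the end of titration (minor)

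*Combined protocol and SAP*

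**What the plan says.** The Aim 3 text in section C.2.d reads "Time to relapse will be calculated as the days between the start of study medication (following titration; day 14"), and runs the interval to the first lapse or to the laboratory stress day, day 40. Kaplan-Meier estimates, log-rank tests and a Cox model with a treatment-by-gender term use this outcome. A second outcome, the longest run of abstinent days during follow-up, has no stated start day.

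The schedule in section C.2.c.5 reads differently:

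- Titration is headed "Lofexidine/Placebo Titration Procedures (Days 8-17").
- Table 2 places first dose at "Days 1 and 2 (Study days 8 and 9"), the fourth of five titration steps at "Days 7 and 8 (Study days 14 and 15"), and the last at "Days 9 and 10 (Study days 16 and 17").
- The next heading is "Medication maintenance and adherence monitoring (Days 18-40").
- Protections Against Risks agrees on the length: "Lofexidine will be titrated over ten days when it is initiated".

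On abstinence at entry, the baseline section says: "Two consecutive UDSs during the baseline week must be negative for illicit opioids in order for the subject to enter the medication treatment". Up to 10 days are allowed for this.

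**The concern.** The sentence gives time zero two labels, the start of medication and the end of titration, and one date, day 14. The date fits neither label, and the labels do not fit each other. An analyst could defensibly start the clock on study day 8, 14, 18 or 21.

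Any start later than randomisation leaves a gap in which participants are on study drug and can already lapse. Abstinence is required for entry to the medication phase. Nothing requires it at day 14, although drug screens three times a week make status around that day available. The supplied text does not say whether a participant who first lapses in the gap is excluded, counted at time zero, or counted only at the next lapse. Exclusion would condition the log-rank and Cox comparisons on something that happens after randomisation and that treatment may influence.

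**Working it through.** **1. Placing day 14.** Medication day 1 is study day 8 (Table 2), so study day = medication day + 7.

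| Possible meaning of time zero | Study day | Medication day | Days to day 40 |
|---|---|---|---|
| First dose | 8 | 1 | 40 − 8 = 32 |
| Day 14 as a study day | 14 | 7 | 40 − 14 = 26 |
| First day after titration | 18 | 11 | 40 − 18 = 22 |
| Day 14 as a medication day | 21 | 14 | 40 − 21 = 19 |

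The stated day 14 cannot be reproduced as either label. The study-day reading is the natural one, because day 40 in the same sentence is a study day: the laboratory sessions are on study days 39 and 40, and medication day 40 would be study day 47. Medication day 14 does come after titration, but it is neither the start of medication nor the first post-titration day.

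If baseline runs to 8, 9 or 10 days, first dose moves to study day 9, 10 or 11. A fixed study day 14 is then 5, 4 or 3 days into medication instead of 6.

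**2. How many first lapses could fall in the gap.** The documents give no lapse rate, so this is illustration only. Assume a constant hazard, a proportion p lapsing within the 32 days to day 40, and randomisation and first dose both on study day 8. Then h = −ln(1 − p)/32, and the share of first lapses in a gap of g days is (1 − exp(−h·g))/p.

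| Clock starts | g | p = 0.30 | p = 0.50 | p = 0.60 |
|---|---|---|---|---|
| Study day 14 | 6 | 0.216 | 0.244 | 0.263 |
| Study day 18 | 10 | 0.352 | 0.390 | 0.415 |
| Study day 21 | 13 | 0.450 | 0.491 | 0.518 |

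For the 6-day gap, the probability of lapsing in it is 0.065 (p = 0.30) to 0.158 (p = 0.60). Out of 136 that is 8.8 to 21.5 participants before attrition. With a 3-day gap and 29 days to day 40, the share is 0.121 to 0.151.

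**3. Effect on the hazard ratio.** These are large-sample Cox limits for two equal arms with piecewise-constant hazards, censored at day 40, under three assumed patterns and a 6-day gap. Ranges are over p = 0.30 to 0.60; ties at time zero are handled by the Breslow method.

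| Assumed pattern | From day 8 | Early lapses as events at time zero | Early lapsers excluded |
|---|---|---|---|
| A. 20% v 10% lapse on days 8–13, then 40% over 26 days in both arms | 0.801 | 0.815 | 1.000 |
| B. Hazard ratio 0.80 throughout | 0.800 | 0.801–0.803 | 0.800 |
| C. No effect before day 14, then 0.80 | 0.843–0.851 | 0.843–0.851 | 0.800 |

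Pattern A implies a hazard ratio of ln(0.90)/ln(0.80) = 0.105/0.223 = 0.47 on days 8–13 and 1.00 afterwards. Counting early lapses at time zero stays within 0.02 of the day-8 result in all three patterns.

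**The case against.** A reader might infer that the planned analysis is biased, or that it could lose a real drug effect. The documents do not support that.

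- The text never says that early lapsers are excluded. If they are counted as events at time zero, almost nothing changes.
- Pattern A, the only one in which the effect disappears, is extreme. It puts the whole benefit on days 8–13, when Table 2 totals are 0.36 to 1.08 mg a day, and none of it from day 18, when the total is 2.16 mg.
- Nor can it be said that no rule exists. The complete analysis plan is held in the Biostatistics Resource Core and was not among the supplied documents; it may cover early lapses.

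Day 14 may be a simple numbering slip. If so, the 22% to 26% figure does not apply, and the share is larger if the intended origin was study day 18 or 21.

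Asking about relapse after titration is also legitimate. Starting at randomisation is a choice of estimand, and pattern C shows that it dilutes an effect that appears only later.

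These points limit the harm and the severity. They do not remove the contradiction between the Aim 3 sentence and the dosing schedule, which would remain even if the fuller plan held a rule for early lapses.

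**Conclusion.** The time-zero definition is wrong as written, and the correction is minor. The mismatch in days rests only on the protocol's own schedule and is certain. Its direct size is the spread in maximum follow-up: 32, 26, 22 or 19 days.

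The statistical consequence is conditional. It depends on how early lapses are handled, which the supplied text leaves open, and on when the drug acts, which is unknown. It may be nil. The shares of 22% to 26%, 35% to 42% and 45% to 52% for clocks starting on study days 14, 18 and 21 rest on the assumed constant hazard and lapse rates.

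Aim 3 is exploratory and the study is powered on Aims 1 and 2, so the primary aims, sample size and power are unaffected. The consecutive-days outcome cannot be declared unaffected, because its follow-up period has no stated start.

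**What to change.** Reconcile the Aim 3 sentence with the titration and maintenance schedule, then:

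1. Set time zero at each participant's randomisation date rather than a fixed study day. Include everyone randomised and count every lapse from then. Randomisation is preferable to first dose because section C.2.c.5 d checks participants before dispensing; someone randomised who fails that check leaves the study without a first dose. It is also the point at which the protocol requires abstinence, and it allows for a baseline of up to 10 days.
2. If the post-titration question is wanted, report it as a landmark analysis from the day that matches the schedule, with a stated rule for earlier lapses.
3. State the same start day for the longest run of abstinent days.

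This takes a few sentences in the Aim 3 text and no new data: daily reports and drug screens three times a week already cover titration. The small statistical cost is the dilution in pattern C, for example 0.84 to 0.85 instead of 0.80, which the landmark analysis would show separately.

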## Power and Sample Size (complete sample size justification available in Biostatistics Resource Core):

The current study is powered on the primary Aims 1 and 2. In the proposed study, response to a laboratory stressor, CREMA cue response and daily use data will be tested using GLMMs (assuming a Gaussian distribution) and the study will be powered to sufficiently address the least of the study treatment effect sizes determined to be clinically meaningful for the study hypothesis. Aim 1: Sinha and colleagues (Sinha, et al 2007), in a small pilot sample, demonstrated that lofexiding in combination with naltrexone attenuated craving and anger in response to laboratory drug and stress cues as compared to naltrexone alone. Results indicate a larger change in opioid craving scores in response to drug-related and stress cues occurs in placebo participants than lofexidine treated participants [Drug related cue response  $\Delta$ =2.2; SDP=2.6; between group Cohen's d=0.85, p<0.05 and stress cues response  $\Delta$ =2.1; SDP=2.4; between group Cohen's d=0.88, p<0.05]. Moreover, Fox and colleagues (2014) conducted a trial of quanfacine in cocaine-dependent individuals and noted stress and craving response to stress and drug-related imagery. They noted significant gender differences across treatment assignment for craving and stress response to drug-related imagery [Craving  $\Delta$ =3.0; SDP=3.8; Treatment x Sex Intx Cohen's d=0.79, p<0.05; Negative Emotion  $\Delta=3.0$ ; SDP=2.9; Treatment x Sex Intx Cohen's d=1.0, p<0.05]. Sample sizes in both the Sinha and Fox studies were somewhat small. Smaller but still clinically relevant effect sizes in an adequately powered study are anticipated. Therefore, a 20% reduction in craving and stress response from the previous studies is anticipated in the current design (Cohen's d=0.64 for the sex x treatment interaction on craving response). Aim 2: Kowalczyk and colleagues (2015), showed that daily life craving reports as measured by EMA were significantly reduced in opioid using participants randomized to clonidine as compared to placebo [6.3% (95% CI=5.6-7.1) vs. 11.8% (10.9-13.0); between group Cohen's *d*=1.6]. To assess the least of the differences anticipated in project 2, a sample size of 39 participants randomized to each female and males across active lofexidine and placebo groups would provide 80% power with a type 1 error rate of 5% to detect the treatment x sex interaction in craving and stress response to laboratory drug based cues (total n=156; 78 per group). We anticipate 25% attrition between randomization and the end of the 5-week active treatment period. Thus, inflating the necessary sample size to 68 participants randomized per treatment group with a total of n=136 randomized participants will provide adequate power.

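### Exploratory Aim 3 states its hypotheses as consecutive days abstinent but names tests only for time to first lapse; the longest abstinent run has no test, and the Gaussian model named for daily use does not suit it

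*Combined protocol and SAP*

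**What the plan says.** All references are to section C.2.d of the combined protocol and SAP.

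- **Status.** The aim is headed "Exploratory Aim 3: To evaluate the impact of lofexidine on illicit drug use in men and women with OUDs".
- **Hypothesis 1.** "Lofexidine will increase the number of consecutive days abstinent as compared to placebo".
- **Hypothesis 2.** The same gain is expected to be larger in women than in men.
- **First derived variable.** Time to relapse runs from day 14 to "the first day of lapse to opioid use or the laboratory stress induction day (day 40").
- **Second derived variable.** In addition, "daily use data will be examined to determine the maximum number of consecutive days abstinent during follow up".
- **Test of treatment.** "Kaplan-Meier estimates and log-rank tests will be used to assess initial relationships between study treatment assignment and relapse".
- **Test of gender.** "Cox proportional hazards models will be developed to assess the differential time to return to use across gender", through an interaction term, followed by checks of proportional hazards.
- **Power and Sample Size.** The study is powered on Aims 1 and 2. The same subsection says that "daily use data will be tested using GLMMs (assuming a Gaussian distribution").

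Two other statements bear on the point. The Aim 2 paragraph says that its Hypothesis 2 models will also be used to look at gender and opioid use, without defining the opioid-use outcome. The opening line of the statistics section places the complete analysis plan in a separate Biostatistics Resource Core document.

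**The concern.** The hypotheses name one quantity and the tests address another that is related to it but not the same. The longest abstinent run is the derived variable whose wording comes closest to the hypotheses. It has no test, no treatment comparison and no gender interaction.

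With two candidate measures and neither assigned to a hypothesis, the choice between them could be made after the results are seen. That includes the gender hypothesis, and gender differences are the study's stated main objective. A treatment that helps people return to abstinence after a lapse would satisfy Hypothesis 1 on one reading, yet would be invisible to a test of first lapse.

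The Gaussian sentence in Power and Sample Size does not fill the gap. It names neither Aim 3 nor the longest run, and a normal error model is a poor match for the data it would cover.

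**Working it through.** The documents give no sample size, power or event count for Aim 3, so there is no plan figure to reproduce. The check sets hypotheses against tests, then asks whether the two measures are interchangeable.

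**Step 1: match each hypothesis to a test (C.2.d, Exploratory Aim 3).**

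| Item | Outcome | Named test |
|---|---|---|
| Hypothesis 1 (treatment) | consecutive days abstinent | none under that name |
| Hypothesis 2 (treatment by gender) | consecutive days abstinent | none under that name |
| Time to relapse | days from day 14 to first lapse, or to day 40 | Kaplan-Meier, log-rank, Cox with interaction |
| Longest abstinent run | maximum over the period | none |

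**Step 2: worked example on the plan's window.** The clock starts on day 14 and ends on day 40, a span of 40 − 14 = 26 days. Take a participant whose only use is on day 16.

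- Time to relapse = 16 − 14 = 2 days.
- Longest run = days 17 to 40 inclusive = 40 − 17 + 1 = 24 days (23 if day 40 is not counted; the plan does not say).

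This person is near the bottom on one measure and near the top on the other.

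**Step 3: where the measures agree.** Time to first lapse is the length of the first abstinent run. Someone who never lapses is at the maximum on both. The measures separate only when a later run exceeds the first one.

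**Step 4: how often that could happen.** The documents do not give the lapse pattern, so this is an illustration on assumed rates. The settings were a 26-day window, a daily chance of lapse of 0.02 to 0.10, and a daily chance of returning to abstinence of 0.1 to 0.9, with and without variation between people and with no dropout. Among those who lapsed, 36% to 68% had a longest run exceeding their time to first lapse. The Spearman correlation between the two measures was 0.37 to 0.97 over everyone and 0.09 to 0.61 among those who lapsed. The width of these ranges shows that the size of the difference cannot be fixed from the documents.

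**Step 5: the Gaussian sentence.** Daily use is a yes/no outcome, or a count if the times used per day from the Time Line Follow-back are taken. Participants enter after two consecutive negative urine screens, so many zero days are plausible. The longest run is one number per person, bounded at about 26 days, with everyone who never lapses piled at the top. A repeated-measures Gaussian model is not a natural choice for either.

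**Related date.** The plan describes day 14 as following titration, but Table 2 in C.2.c.5 runs titration through study day 17. Both measures depend on the start day, so these passages must be reconciled. The contrast does not hinge on it: with a clock starting on day 18, use on day 20 only gives 20 − 18 = 2 days against a run of 40 − 21 + 1 = 20 days.

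**The case against.** The strongest reply is that the hypotheses do not say longest or maximum. This is a relapse-prevention design whose participants enter abstinent, so days from clock start to first lapse can fairly be read as the number of consecutive days abstinent. The longest run is introduced only as an addition. On that reading the named tests do address the hypotheses. This stands, and it is why rewording the hypotheses is the natural repair. It does not remove the ambiguity, because the plan also derives the longest run and does not say which measure decides.

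A reader might infer that the abstinence hypotheses are never tested at all. The documents do not support that. Time to first lapse captures the first abstinent run, the Aim 2 models are also to look at opioid use, and the complete analysis plan is held in a document not included here.

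A reader might also infer that the Aim 3 and power paragraphs contradict each other. They need not: survival methods for time to relapse and a mixed model for daily use can coexist. What is missing is a statement of which outcome each covers. The Gaussian choice is a separate weakness.

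Finally, it is tempting to make the longest run the main measure and the survival analysis supportive. That would be a trade-off, not a plain correction. The plan expects 25% attrition, which is 0.25 × 136 = 34 participants. A survival analysis can censor them, whereas a longest run is simply cut short at dropout unless a rule is written.

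**Conclusion.** The point holds as a specification gap. Exploratory Aim 3 does not say which measure tests Hypotheses 1 and 2, names tests only for time to first lapse, and derives the longest abstinent run with no test. The measures are not interchangeable for people who lapse (2 days against 24 in the worked example). How much this would matter across the trial depends on a lapse pattern that the documents do not give.

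The Gaussian model named for daily use should be corrected in any case. That judgement rests on the outcome being yes/no, a count or a bounded run. The expectation that use days will be sparse is an inference from abstinent entry, not a figure in the plan.

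Severity is minor. Aim 3 is labelled exploratory, the study is powered on Aims 1 and 2, and no primary conclusion changes.

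**What to change.** 1. Keep the Kaplan-Meier, log-rank and Cox analyses. Reword Hypotheses 1 and 2 as time to first lapse, that is, days continuously abstinent from the start of the clock. State how dropouts are censored, and note that censoring assumes dropout is unrelated to imminent lapse.
2. If the longest run is also to be tested, name it as a secondary measure. Use a proportional-odds or rank-based model with treatment, gender and their interaction. Define its window, and give a rule for dropout and missing days.
3. In Power and Sample Size, remove daily use data from the Gaussian sentence, or specify a logistic mixed model for daily yes/no use.
4. Reconcile the day-14 clock start with the titration period in Table 2.

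The cost is SAP wording and, if item 2 is taken up, one extra model on data already being collected.
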